#### **Documented symptomatic hypoglycemia**

Documented symptomatic hypoglycemia is an event during which typical symptoms of hypoglycemia are accompanied by a measured plasma glucose concentration of  $\leq 70$  mg/dL (3.9 mmol/L). Clinical symptoms that are considered to result from a hypoglycemic episode can include (but are not limited to): increased sweating, nervousness, asthenia, tremor, dizziness, increased appetite, palpitations, headache, sleep disorder, confusion, seizures, unconsciousness, and coma.

In the eCRF, documented symptomatic hypoglycemia is identified based on information captured in the “Symptomatic hypoglycemic event information” page as those

- not ticked “Subject was Not Capable of Treating Self and Required Assistance” to the question “Countermeasure Administration” and
- ticked “Yes” to the question “Were Symptoms Present” and
- with a measured plasma glucose value before countermeasure  $\leq 70$  mg/dL (3.9 mmol/L).

### **Asymptomatic hypoglycemia**

Asymptomatic hypoglycemia: Asymptomatic hypoglycemia is an event not accompanied by typical symptoms of hypoglycemia but with a measured plasma glucose concentration less than or equal to 70 mg/dL (3.9 mmol/L).

- not ticked “Subject was Not Capable of Treating Self and Required Assistance” to the question “Countermeasure Administration” and
- ticked “No” to the question “Were Symptoms Present” and
- with a measured plasma glucose value  $\leq 70$  mg/dL (3.9 mmol/L).

### **Probable symptomatic hypoglycemia**

Probable symptomatic hypoglycemia is an event during which symptoms of hypoglycemia are not accompanied by a plasma glucose determination, but was presumably caused by a plasma glucose concentration less than or equal to 70 mg/dL (3.9 mmol/L); symptoms treated with oral carbohydrate without a test of plasma glucose.

In the eCRF, probable symptomatic hypoglycemia is identified based on information captured in the “Symptomatic hypoglycemic event information” page as those

- not ticked “Subject was Not Capable of Treating Self and Required Assistance” to the question “Countermeasure Administration” and
- ticked “Yes” to the question “Were Symptoms Present” and
- ticked “Yes” to the question “Was Any Countermeasure Given for the Hypoglycemic Event?” and
- ticked “Yes” to the question “Did this countermeasure lead a significant improvement or prompt recovery?” and
- with no plasma glucose value before countermeasure.

### **Relative hypoglycemia**

Relative hypoglycemia: Relative hypoglycemia recently termed “pseudo-hypoglycemia” is an event during which the person with diabetes reports any of the typical symptoms of hypoglycemia, and interprets the symptoms as indicative of hypoglycemia, but with a measured plasma glucose concentration greater than 70 mg/dL (3.9 mmol/L), but approaching this level.

- not ticked “Subject was Not Capable of Treating Self and Required Assistance” to the question “Countermeasure Administration” and
- ticked “Yes” to the question “Were Symptoms Present”
- with a measured plasma glucose value before countermeasure  $> 70$  mg/dL (3.9 mmol/L),

Symptomatic hypoglycemia events fulfilling the criteria of a SAE will also be recorded on AE and SAE forms in eCRF.

### **2.1.4.2 Adverse events variables**

#### ***Adverse event observation period***

- Pre-treatment adverse events are AEs that developed or worsened or became serious during the pretreatment period.
- Treatment-emergent adverse events are AEs that developed or worsened (according to the Investigator's opinion) or became serious during the TEAE period.
- Post-treatment adverse events are AEs that developed or worsened or became serious during the post-treatment period.

All AEs (including SAEs and AEs with prespecified monitoring) will be coded to a lower-level term (LLT), preferred term (PT), high-level term (HLT), high-level group term (HLGT), and associated primary system organ class (SOC) using the version of Medical Dictionary for Regulatory Activities (MedDRA) currently in effect at Sanofi at the time of database lock.

Record the occurrence of AEs (including SAEs and AEs with prespecified monitoring) from the time of signed informed consent until the end of the study.

#### **AESI include:**

- Pregnancy
- Symptomatic overdose
- Alanine aminotransferase (ALT) increase >3X upper limit of normal (ULN) (per related decision chart in Appendix C of protocol)
- prolongation of QTc interval  $\geq 500$  ms (automatic measurement and confirmed by a manual reading by the Investigator or a physician delegated by the Investigator using the Fridericia formula for correcting QT)
- sinus tachycardia (defined as confirmed sinus tachycardia [heart rate >100 bpm] in supine position reported at more than 2 visits) and associated with a concomitant increase, from baseline, in heart rate of  $\geq 15$  beats per minute
- Severe allergic or allergic-like reaction (except local reactions at site of injection)
- Calcitonin  $\geq 20$  pg/mL: events recorded on the AE form for increased calcitonin and its associated complementary form.
- Amylase or lipase >2 x ULN
- Metabolic acidosis

Note that all AESI are identified by the corresponding AECAT variable in the AE raw dataset and/or other specific form as listed in the table below.

**Table 3 - Summary of AESI reporting instructions**

Event category	Reporting timeframe	Specific events in this category	Case Report Form completion		
			AE form	Safety Complementary Form	Other specific forms
Adverse Event of Special Interest	Expedited (within 24 hours)	Pregnancy	Yes	Yes	Yes
		Symptomatic overdose	Yes	Yes	Yes
		Increase in alanine transaminase (ALT)	Yes	Yes	Yes
		Prolongation of QTc interval (automatic measurement) $\geq 500$ ms	Yes	Yes	No
		Persistence of sinus tachycardia per definition in Section 2.1.4.2 and associated with a concomitant increase, from baseline, in heart rate of $\geq 15$ beats per minute	Yes	Yes	No
		Severe allergic or allergic-like reaction (except local reactions at site of injection)	Yes	Yes	Yes
		Calcitonin $\geq 20$ pg/mL	Yes	Yes	Yes
		Amylase/lipase $> 2 \times \text{ULN}$	Yes	Yes	Yes
		Metabolic acidosis	Yes	Yes	No

**Other AEs to be separately analyzed include:**

- Major cardiovascular events: events adjudicated as major cardiovascular events by CAC:
  - Death
  - MI/UA requiring hospitalization
  - Congestive heart failure requiring hospitalization
  - Coronary Revascularization
  - Arrhythmia
  - Stroke

Adverse events sent for adjudication for major cardiovascular events will be identified by the corresponding AECAT variable in the AE raw dataset and/or other specific form and/or adjudication form.

- Pancreatic events:
  - Pancreatitis adjudicated by the Pancreatic Safety Assessment Committee (PSAC) as: 1) acute pancreatitis, 2) acute on chronic pancreatitis, 3) chronic pancreatitis, 4) unknown pancreatitis.
  - Pancreatic neoplasms adjudicated by the PSAC

Adverse events sent for adjudication for pancreatitis and/or Pancreatic neoplasms will be identified by the corresponding AECAT variable in the AE raw dataset and/or other specific form and/or adjudication form.

- Local tolerability at injection site: identified by searching the term “injection site” in the PTs coded from the investigator reported terms.

#### **2.1.4.3 Deaths**

The deaths observation period are per the observation periods defined above.

- Death on-study: deaths occurring during the on-study observation period
- Death on-treatment: deaths occurring during the TEAE period
- Death post-study: deaths occurring after the end of the study

#### **2.1.4.4 Laboratory safety variables**

Clinical laboratory data consists of blood analysis (including hematology and clinical chemistry, amylase, lipase, calcitonin) and urinalysis (albumin/creatinine ratio). Clinical laboratory values will be summarized in both standard international units and conventional units.

The laboratory data will be collected at designated visits (see study flowchart in [Appendix C](#). The following laboratory data will be measured at a central laboratory and used as safety endpoints:

- Hematology
  - Red blood cells, platelets: hemoglobin, hematocrit, red blood cells (erythrocytes) count, platelets count.
  - White blood cells: white blood cells count, and differential counts (neutrophils, lymphocytes, monocytes, basophils, and eosinophils).
- Clinical chemistry
  - Electrolytes: sodium, potassium, calcium, phosphorus.
  - Renal function: creatinine, calculated eGFR, cystatin C, uric acid.
  - Liver function: alanine aminotransferases (ALT), aspartate aminotransferases (AST), alkaline phosphatase (ALP), gamma-glutamyl transpeptidase (GGT), total bilirubin (and, in case of values above the normal range, differentiation in conjugated and non-conjugated bilirubin).
- Thyroid panel: Thyroid-stimulating hormone (TSH), Total Triiodothyronine (T3) and Free Thyroxine (FT4).
- Pancreatic enzymes: lipase, amylase.
- Serum calcitonin.
- Urine analysis: albumin/creatinine ratio.
- Urinary free-cortisol and creatinine based on 24-hour urine sample in some patients, 24-hr free-cortisol/creatinine ratio will be derived for these patients.

Lipid parameters (fasting): total cholesterol, triglycerides, LDL-C, and HDL-C are presented as efficacy parameters in [Section 2.1.3.2](#).

Other laboratory data not mentioned above (serology tests (hepatitis B antigen, hepatitis C antibodies), serum pregnancy test, serum follicle-stimulating hormone [FSH], and estradiol) will not be defined as safety endpoints (collected as per study flowchart in [Appendix C](#)).

Technical formulas are described in [Section 2.5.1](#).

#### **2.1.4.5 Vital signs variables**

Vital signs include supine heart rate (bpm) and sitting systolic and diastolic blood pressures (mmHg).

#### **2.1.4.6 Physical examination**

A exam will be performed at Visit 1 (Screening), Visit 4 (baseline), Visit 9 (Week 8), Visit 10 (Week 14), and at final assessment (Visit 12 at Week 26, primary endpoint assessment visit). “Normal”, “Abnormal” or “Not done” as determined by the Investigator will be reported in the eCRF. Any abnormality related to physical examination will be reported in the eCRF “Adverse Event” page or “Medical History” page.

#### **2.1.4.7 Electrocardiogram variables**

Standard 12-lead ECGs are recorded at Week -3, 0 (Day 1), 4, Visit 10 (Week 14), and on Visit 12 (Week 26, primary endpoint assessment visit). A single 12-lead ECG printout with heart rate, PR, QRS, QT, QTc automatic correction evaluation (by the ECG device) will be generated. ECG status of “normal” or “abnormal” will be reported in the eCRF as determined by the Investigator.

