
STUDY POPULATION Main selection criteria
	
Inclusion criteria:
 
 • Patients with type-2 diabetes mellitus (T2DM) for at least 3 months before the screening visit. • On diet/exercise and/or treatment with metformin (stable dose of ≥1500 mg/day or maximal tolerated dose) for at least 3 months prior to screening. • Signed informed consent. 
Exclusion criteria:
 
 • At screening, patient's age < legal age of adulthood or >80 years. • HbA_{1c} at screening visit <7.0% or >10.0%.

	
 • BMI <25 kg/m² or >45.0 kg/m². • Pregnant or lactating women. • Women of childbearing potential (WOCBP) not protected by highly-effective method(s) of birth control and/or who are unwilling or unable to be tested for pregnancy (see contraceptive guidance in Appendix A). • Diagnosis of type-1 diabetes mellitus. • FPG >15 mmol/L (270 mg/dL) measured by the central laboratory at screening (Visit 1), and confirmed (>15 mmol/L [270 mg/dL]) by a repeat test before randomization. • Treatment with glucose-lowering agents(s) other than metformin, currently or within the 3 months prior to screening. • Previous insulin use, except for episode(s) of short-term treatment (≤15 consecutive days) for intercurrent illness or pregnancy, or use of insulin within the last 6 months. • Contraindication(s) to metformin use. • Contraindication(s) to liraglutide use. • Significant change in body weight in the 3 months before screening. • Poorly controlled hypertension (a resting systolic blood pressure [SBP] >160 mm Hg and/or diastolic blood pressure [DBP] >95 mm Hg at screening). • History of long QT syndrome and/or QTc more than 450 ms at screening visit. • History of pancreatitis or pancreatectomy. • History of weight loss surgery. • Personal or immediate family history of medullary thyroid cancer (MTC) or genetic conditions that predispose to MTC. • Any prior exposure to drugs belonging to the class of GLP-1 receptor agonists or GLP-1 analogs. • Contraindications or known hypersensitivity reaction to glucagon.

Total expected number of patients
	
Approximately 270 randomized patients. Approximately 70 sites anticipated.

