9.2.2.6 Electrocardiogram variables

9.2.2.6.1 Twelve-lead electrocardiogram

Electrocardiogram data will be assessed by the Investigator based on the automatic device reading in the morning before the IMP intake.

Standard 12-lead ECGs are recorded after at least 10 minutes in supine position (10-second recording at 25 mm/s, 10 mm/mV) at Week -3, 0, 4, 14, and 26. The electrodes will be positioned at the same place for each ECG recording throughout the study.

Each ECG will consist of a 10-second recording of the 12 leads simultaneously, leading to:

A single 12-lead ECG (25 mm/s, 10 mm/mV) printout with heart rate, PR, QRS, QT, QTc automatic correction evaluation (by the ECG device), including date, time, initials, and number of the subject, signature of the research physician.

The Investigator's medical opinion and automatic values will be recorded in the eCRF. This printout and/or digital storage will be retained at the site.

Please also refer to [Section 10.3](#) and the "General Guidelines for reporting AEs" in [Section 10.4.3](#).

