10.4.1.3 Adverse event of special interest

An AESI is an AE (serious or nonserious) of scientific and medical concern specific to the Sponsor's product or program, for which ongoing monitoring and immediate notification by the Investigator to the Sponsor is required. Such events may require further investigation in order to characterize and understand them. Adverse events of special interest may be added, modified or removed during a study by protocol amendment.

- Pregnancy of a female patient entered in a study as well as pregnancy occurring in a female partner of a male subject entered in a study with IMP/NIMP:
 - Pregnancy will be recorded as an AESI with immediate notification in all cases,
 - It will be qualified as an SAE only if it fulfills one of the seriousness criteria (see [Section 10.4.1.2](#)),
 - In the event of pregnancy in a female participant, IMP should be discontinued,
 - Follow-up of the pregnancy in a female participant or in a female partner of a male participant is mandatory until the outcome has been determined.
- Symptomatic overdose (serious or nonserious) with IMP/NIMP: An overdose (accidental or intentional) with the IMP/NIMP is an event suspected by the Investigator or spontaneously notified by the patient (not based on systematic pen count) and defined as:
 - For SAR 425899 and matching placebo: any dose greater than the planned dose administered per day during this clinical trial,
 - For Liraglutide: any dose greater than the planned dose administered per day during this clinical trial,

- For metformin: any dose greater than the recommended dose administered per day during this clinical trial.
- Of note, asymptomatic overdose has to be reported as a standard AE.
- Increase in ALT >3 x ULN (refer to related decision chart in [Appendix C](#)).
- Other project specific AESIs:
 - In the event of prolongation of QTc interval (automatic measurement) ≥ 500 ms, confirmed by a manual reading by the Investigator or a physician delegated by the Investigator using the Fridericia formula for correcting QT, the subject should be placed under supervision in a specialized setting. Investigational medicinal product administration must be stopped and appropriate blood samples collected. Subsequent ECG monitoring of the subject should then be performed on a regular and clinically responsible basis until the QTc interval returns to a safe value as determined by the Investigator in agreement with the Sponsor,

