11.4.3.5 Analyses of 12 lead electrocardiogram status

ECG (12-lead ECG)

For HR, PR-, QRS- and QT-intervals and corrected QT (QTc), number and percentage of patients with a PCSA at any evaluation during the on-treatment period will be summarized by treatment group. The summaries will include patients in the safety population who have at least one parameter to be analyzed during the on-treatment period. When the PCSA definition involves the change from the baseline value, patients need also to have a baseline value to be included in the summaries.

Descriptive statistics will be used to summarize the results and the changes from baseline by visit and for the last on-treatment value within each treatment group.

Tabular and graphical methods may be used to present the results for parameters of interest.

Listings will be provided with flags indicating the PCSA values.

A listing of subjects with at least one abnormality in qualitative assessment (ie, abnormal ECG) during the on-treatment period will be also provided.

24-hours Holter ECG

For 24-hour average and night time average heart rate, descriptive statistics will be used to summarize the results and the changes from baseline by visit and for the last on-treatment value within each treatment group.

Tabular and graphical methods may be used to present the results for parameters of interest.

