#### **2.4.5.6 Analyses of 12 lead electrocardiogram variables**

The summary statistics (including number, mean, median, Q1, Q3, standard deviation, minimum and maximum) of all 12 lead ECG variables (HR, PR, QRS, QT, QTc and changes from baseline) will be calculated for each applicable visit or study assessment (screening, baseline, postbaseline time points, last on-treatment value) by treatment group. For parameters HR, PR, QRS, QT, QTc mean changes from baseline with the corresponding standard error will be plotted over time (at same time points) in each treatment group.

The incidence of PCSAs at any time during the treatment-emergent adverse event period will be summarized by treatment group irrespective of the baseline level and/or according to the following baseline status categories:

- Normal/missing
- Abnormal according to PCSA criterion or criteria

The summaries will include patients in the safety population who have at least 1 assessment performed during the TEAE period. When a PCSA definition involves a change from baseline value, patients must also have a baseline value to be included in the summaries.

A listing of patients with at least 1 post-baseline PCSA will be provided and will display the patient's profile over time of all vital sign parameters. Individual data listings will include the following flags:

- Baseline values will be flagged "B",
- Parameter values reaching a PCSA limit will be flagged (+, ++, -, or -- depending of the direction and level of the abnormality).

A listing of subjects with at least one abnormality in qualitative assessment (ie, abnormal ECG) during the TEAE will be also provided.

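### QTc is summarised as the ECG device's automatic value with no formula named; a Fridericia QTc derived from the recorded QT and heart rate would guard against a heart-rate artefact

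*SAP*

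**What the plan says.** **Source of QTc.** SAP 2.1.4.7 describes one 12-lead printout per visit, on which "QTc automatic correction evaluation (by the ECG device) will be generated". Protocol 9.2.2.6.1 agrees: "Electrocardiogram data will be assessed by the Investigator based on the automatic device reading", and the investigator's "medical opinion and automatic values will be recorded in the eCRF".

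**Use of QTc.** SAP 2.4.5.6 gives by-visit summary statistics for "all 12 lead ECG variables (HR, PR, QRS, QT, QTc and changes from baseline" and plots mean changes from baseline. Both SAP 2.4.5.6 and protocol 11.4.3.5 count potentially clinically significant abnormalities (PCSAs); the protocol wording covers "corrected QT (QTc), number and percentage of patients with a PCSA". Neither section names a formula or recalculates QTc.

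**Where a formula is named.** Fridericia is the only correction named in either document. It appears in the adverse-event-of-special-interest (AESI) rule (protocol 10.4.1.3, repeated in SAP 2.1.4.2). An automatic QTc of 500 ms or more is the trigger, to be "confirmed by a manual reading by the Investigator or a physician delegated by the Investigator using the Fridericia formula for correcting QT".

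**Setting.** The protocol synopsis says "Approximately 70 sites anticipated". Protocol 9.2.2.6.2 provides a reading centre for Holter recordings; no such arrangement is stated for the 12-lead ECG. Protocol 5.2 and SAP 1.2.2 place heart-rate change by ECG and Holter within a main secondary objective.

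**The concern.** QT shortens as heart rate rises, and a correction formula is meant to remove that dependence. Formulas differ in how much they remove. When heart rate is stable the choice matters little for change from baseline. When a treatment raises heart rate, a formula that over-corrects at higher rates turns part of the rate effect into an apparent QTc increase.

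The sponsor plainly regards a heart-rate rise as possible. Besides the objective, persistent sinus tachycardia with a rise of at least 15 bpm is an AESI (protocol 10.4.1.3), and exposure modelling against heart rate is planned at the PK/PD interim (SAP section 3).

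The placebo group does not remove such an artefact. If heart rate rises on active drug and not on placebo, the artefact appears as a treatment difference, and it would follow dose if the heart-rate rise does. At stake is how the QTc means, plots and abnormality counts are read.

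**Working it through.** The plan states no figure on this point, so there is nothing to reproduce. The check sizes the possible artefact.

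**Formulas.** RR = 60/HR in seconds. Fridericia: QTcF = QT/RR^(1/3). Bazett: QTcB = QT/RR^(1/2). Dividing one by the other gives

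QTcB = QTcF × (HR/60)^(1/6).

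**Inputs, all assumed.** The documents give neither the device formula nor an expected heart-rate rise. True QTcF is held at 410 ms and heart rate starts at 70 bpm.

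| Heart rate | QT = 410 × (60/HR)^(1/3) | QTcF | QTcB = 410 × (HR/60)^(1/6) | Apparent change, Bazett |
|---|---|---|---|---|
| 70 bpm | 389.5 ms | 410 ms | 420.7 ms | – |
| 75 bpm | 380.6 ms | 410 ms | 425.5 ms | +4.9 ms |
| 80 bpm | 372.5 ms | 410 ms | 430.1 ms | +9.5 ms |

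**Range.** The same calculation with constant QTcF between 400 and 450 ms and baseline heart rate between 65 and 75 bpm gives the apparent change in QTc below. Two linear corrections are included for comparison: Framingham, QT + 154 × (1 − RR), and Hodges, QT + 1.75 × (HR − 60), both in ms.

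| Heart-rate rise | Fridericia | Bazett | Framingham | Hodges |
|---|---|---|---|---|
| 5 bpm | 0 | +4.5 to +5.7 ms | −1.2 to +0.7 ms | −1.9 to +0.8 ms |
| 10 bpm | 0 | +8.8 to +11.0 ms | −2.6 to +0.8 ms | −2.9 to +2.3 ms |
| 15 bpm | 0 | +12.8 to +16.1 ms | −4.1 to +0.6 ms | −3.1 to +4.4 ms |

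The zero for Fridericia holds by construction, because QTcF is the quantity held fixed. The artefact is therefore mainly a Bazett matter.

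**Effect on threshold counts.** From QTcF = QTcB × (60/HR)^(1/6), a Bazett reading of 500 ms equals a Fridericia value of 476.6 ms at 80 bpm and 459.2 ms at 100 bpm. A Bazett reading of 450 ms equals 428.9 ms at 80 bpm. Counts above a fixed limit would shift with the formula as well as the means.

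**Can it be corrected from data already planned?** Yes. QT and heart rate are on the same printout (SAP 2.1.4.7), the automatic values go into the eCRF (protocol 9.2.2.6.1), and both are already analysis variables in SAP 2.4.5.6.

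**The case against.** The case for leaving the plan alone has several sound parts.

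- **Mixed formulas are not shown.** A reader might infer that sites use different devices with different corrections. The documents give only the number of sites. They are silent on whether machines are supplied or standardised. Even with mixed formulas, change from baseline is within patient, so a fixed offset largely cancels if a site keeps one device.
- **The AESI rule is not contradicted.** A reader might say that the trial's own safety rule rests on Fridericia while its tables do not. The trigger is the automatic value, and Fridericia only confirms it. That is a two-step rule, not an inconsistency.
- **Appendix A is not in the text available.** It may name a correction for the PCSA criteria. That would settle the abnormality tables, but the by-visit means and plots would still use the recorded device value unless QTc were recalculated.
- **The analysis is descriptive.** SAP 2.4.5 plans no systematic testing of safety data. Raw QT and heart rate are summarised beside QTc, so a careful reader could see a QTc rise accompanied by a faster rate and a shorter QT (in the example above, QT falls by about 17 ms for a 10 bpm rise).
- **Direction and size.** For a drug that raises heart rate, Bazett gives a false alarm, not a hidden prolongation. ECGs are recorded before dosing. Protocol 9.2.2.1 equates 3 days with about five half-lives (72/5 = 14.4 hours), so these tracings lie near trough, another reason not to presume a large rise.

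All of this stands and limits the claim. It does not answer the main point: the stated source of QTc leaves its rate correction open in a trial that studies heart rate, and the data to close the gap are already collected.

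**Conclusion.** The point holds as a low-cost improvement to a descriptive safety readout. The analysed QTc is, on a fair reading of SAP 2.1.4.7 with protocol 9.2.2.6.1, the device's automatic value under an unnamed correction.

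The size is conditional. If devices use Bazett and the drug raises heart rate, QTc would show an apparent rise of about 5 ms for 5 bpm and 9.5 ms for 10 bpm, at a constant QTcF of 410 ms from 70 bpm. If only some devices use Bazett, the effect on group means is diluted accordingly. If all use Fridericia, it is nil.

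It would be tempting to conclude that the trial's QT assessment is unreliable whichever formula the devices use. The documents do not support that: no formula is shown to be wrong, none is shown to vary between sites, and no formal QT conclusion is planned. The primary endpoint, the secondary efficacy endpoints and the directly measured heart-rate results are unaffected.

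**What to change.** In SAP 2.1.4.7, define QTcF = QT/(RR)^(1/3), with RR = 60/HR in seconds, derived for every patient and visit from the recorded QT and heart rate. In SAP 2.4.5.6, use QTcF for the by-visit summaries and the plots of change from baseline. Use it also for the QTc abnormality tables, after checking that this agrees with the PCSA criteria in Appendix A. Keep the device QTc in the listings. Comparing it with the derived value would also show which correction each device applied.

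Eligibility, AESI and stopping rules stay as written; the change concerns only how recorded values are summarised.

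The cost is one derived variable and a few lines of SAP text, with no new data. The change removes differences due to the formula. It does not improve the QT measurement itself, which remains an automatic reading from a single 10-second tracing.
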